4.2 Endpoints

4.2.1 Primary Endpoint

The primary endpoint for this study is the change in measurements of tear volume over time as measured by the UHR-OCT following the administration of P-321 Ophthalmic Solution and Placebo in subjects with tear deficient dry eye disease.

4.2.2 Secondary Endpoints

The secondary endpoints are to:

- assess changes in lower tear meniscus height by Keratograph 5M
- compare lower tear meniscus height measurements between UHR-OCT and Keratograph 5M

- assess the duration of action of P-321 Ophthalmic Solution
- compare the pharmacodynamic activity of different strengths of P-321 in subjects with tear-deficient dry eye
- monitor safety and tolerability of P-321 Ophthalmic Solution

4.2.3 Safety and Tolerability Endpoints

Safety endpoints include: AEs, biomicroscopy and external eye examination and comfort assessment (after each in-clinic dose).

4.3 Duration of Participation

The study will consist of three study visits: A Screening Visit (Visit 1), and two Treatment Visits (Visit 2 and Visit 3). The duration of the study may be up to 23 days. The start of each visit will take place between 8:00AM and 11:00 AM and at approximately the same time as Visit 1.

Visit 1 is expected to last approximately 2 hours and Visits 2 and 3 are expected to last approximately 7 hours.

5 SELECTION AND WITHDRAWAL OF SUBJECTS

5.1 Subject Inclusion Criteria

Subjects must meet the following criteria at Screening to be enrolled in the study:

1. Provide written informed consent
2. Male or female subjects aged 18 to 80 years
3. Are willing and able to follow instructions and can be present for the required study visits for the duration of the study
4. Have a history of predominantly tear-deficient dry eye of mild to moderate severity, in both eyes, supported by a previous clinical diagnosis
5. Subjects must have in at least one eye an average tear meniscus height (TMH) of the lower eye lid of 210 μm or less as assessed by UHR-OCT
6. Have normal lid anatomy
7. Female subjects of child bearing potential must have a negative serum pregnancy test at Screening and agree to use a medically acceptable form of birth control (e.g., intrauterine device, birth control pill, patch or subcutaneous implant, condoms, diaphragm, or abstinence) throughout the duration of the study. Females who are breast feeding an infant are not eligible to participate in the study.
8. Subjects must:
 - a. Remain on current medications for the duration of the study
 - b. Be on the current medication regimen at least during the past 28 days
 - c. Be able to withhold ocular topical medications, including artificial tears, topical steroids, Restasis[®], Xiidra[®], autologous serum, and lid wipes and scrubs on visit days while in the clinic, and for at least 6 hours after dosing with study medication
 - d. If they are contact lens wearers, be able to withhold wearing contact lenses on visit days, while in the clinic, and for at least 6 hours after dosing

5.2 Subject Exclusion Criteria

Subjects who meet any of the following criteria at Screening or during the study will be excluded from the study.

1. Have an identifiable or suspected dry eye caused by pharmacologic, post-traumatic, or post-surgical condition
2. Have undergone refractive eye surgery (e.g., LASIK) in either eye during the past 12 months
3. Have undergone uncomplicated cataract surgery in either eye during the past 3 months
4. Have undergone previous eyelid surgery in either eye (e.g., blepharoplasty, ptosis repair). External blepharoplasty, not resulting in exposure or abnormal blinking, will be allowed.
5. Have lid irregularities or deformities
6. Have severe corneal surface irregularities

7. Have undergone botulinum toxin (Botox™ or equivalent) injection in the periocular area within 3 months prior to Visit 1
8. Have a history of glaucoma or IOP > 25 mmHg at the Screening Visit (Visit 1) or a history of elevated IOP within the past year
9. Subjects that have a systemic, multi-organ disease (with the exception of subjects with SS or GVHD) requiring active medical or surgical treatment are excluded, **except** if the following conditions are met:
 - a. the condition is chronic (> 1 years' duration), stable, of mild severity and adequately controlled
 - b. the condition does not or is unlikely to have ocular manifestations
 - c. the condition is one of the following:
 - i. essential hypertension
 - ii. coronary artery disease
 - iii. Type II diabetes mellitus without diabetic retinopathy
 - iv. thyroid dysfunction without thyroid eye disease
 - v. non-morbid obesity
 - vi. remote history of cancer (> 5 years from diagnosis)
10. Have punctal plugs, punctal occlusion, or history of nasolacrimal duct obstruction or wear scleral lenses,
11. Stevens-Johnson syndrome, ocular cicatricial pemphigoid, or other ocular cicatrizing disorders
12. Past or present exposure keratopathy, neurotrophic keratopathy, lagophthalmos, or trichiasis
13. Subjects taking the following medications within 14 days of Visit 1 or during the study are excluded
 - a. Oral, nasal and ocular antihistamines
 - b. Oral or topical secretagogues such as pilocarpine and Evoxac
 - c. Topical anti-glaucoma medications
14. History of allergies to any of the components of the study medication
15. Are pregnant or breast feeding an infant.
16. Have any significant illness that, in the opinion of the Principal Investigator (PI), could interfere with the study parameters
17. Use of any investigational product or device within 28 days prior to the Screening Visit or during the study
18. Are unable in the opinion of the PI to comply fully with the study requirements or to complete the study

5.3 Randomization Criteria

At Visit 2 (First Treatment Visit) and Visit 3 (Second Treatment Visit), an eligible subject must:

1. Continue to meet all clinical inclusion/exclusion criteria as defined in [Section 5.1](#) and [Section 5.2](#), with the exception of the inclusion criteria #5 (UHR-OCT measurement)
.

A log will be maintained at the sites for those subjects that do not meet eligibility criteria. Minimally this log will include the subject's age, sex and race and the reason that they were not eligible. Screen failure data will not be collected in the clinical database.

5.4 Study Eye

The Study eye will be the eye that meets entry criteria as defined in [Section 5.1](#), [Section 5.2](#), and [Section 5.3](#). If both eyes meet entry criteria, the study eye will be the eye with the lower average TMH by OCT. If both eyes have the same average TMH, then the qualifying study eye will be the **right eye**.

5.5 Subject Withdrawal Criteria and Stopping Rules

Treatment may be discontinued and the subject withdrawn at any time during the study at the discretion of the investigator, Medical Monitor or Parion Sciences for any reason including but not limited to occurrence of an AE which precludes subsequent participation, withdrawal of Informed Consent, or requirement of an ocular surgery or intervention. Also in the event that a woman becomes pregnant while participating on the study, she will be withdrawn from the study. In the event that discontinuation of treatment is necessary, the investigator will make every attempt to complete all subsequent safety assessments and the Early Termination Visit. The reason for premature discontinuation should be entered onto the paper case report form (CRF). Subjects who withdraw from the study will be replaced.

Additionally, the trial or parts of the trial may be discontinued by Parion Sciences, Inc. or at the recommendation of the Investigator or Medical Monitor after consultation with Parion. This may be based on a significant number of AEs of a similar nature that warrant such action or at the request of Parion Sciences, Inc.

6 PROCEDURES

The procedures performed for this study are listed below. The times indicated in the following sections and Appendices are based on the visit starting in the AM with each visit starting at a consistent timeframe relative to Visit 1.

6.1 Visit 1: Screening (3 to 9 days prior to Visit 2 – Randomization)

The subject should initiate screening procedures within 14 days of signing the ICF. Prior to conducting study procedures, informed consent will be obtained.

The following procedures will be completed at Visit 1 which will start between 8:00AM and 11:00AM:

- Review eligibility criteria
- Review of the medical history
- Review concomitant medication history in the past 28 days
- Administer ocular symptom questionnaires (SPEED, OSDI, and SANDE Part 1 only) before other procedures
- Biomicroscopy and external eye examination
- Visual acuity
- Abbreviated physical exam (including respiratory, cardiovascular, musculoskeletal, gastrointestinal, dermatological)
- Vital signs (pulse, blood pressure, temperature and respiration rate) and height and weight
- Conduct pretreatment measurements in both eyes by UHR-OCT and Keratograph 5M three times in one hour (at 0 minutes, 30 ± 10 minutes and 60 ± 20 minutes). NOTE: throughout the study, UHR-OCT will be conducted first, immediately followed by Keratograph 5M.
- Tear osmolarity
- TBUT
- Assessment of meibomian glands
- Corneal staining
- Conjunctival staining
- Schirmer's test
- IOP
- Collect blood for hematology, chemistry and pregnancy tests

Monitoring of adverse events will begin from the time the Informed consent is signed

Eligible subjects will be instructed to return to the clinic between 3 and 9 days for the first treatment (Visit 2, First Treatment Visit) with the visit occurring in the AM, at approximately the same time of day as Visit 1. Subjects will be reminded not to use ocular medications or wear contact lenses on the day of Visit 2.

6.2 Visit 2: First Treatment Visit (3 -9 days after Visit 1)

The following procedures will be completed at Visit 2 which will take place between 8:00AM and 11:00 AM and at approximately the same time as Visit 1:

- Subjects will be asked to remain on site through this visit and limit use of devices with video display screens.
- Confirm continued eligibility through review of inclusion and exclusion criteria as outlined in [Sections 5.1 and 5.2](#) of the protocol with the exception of the inclusion criteria #5 (UHR-OCT dry eye).
- Review of concomitant medications and medical changes since last visit
- Administer symptom questionnaires (SPEED, OSDI, and SANDE Part 1 and Part 2) before other procedures and before dosing
- Assess adverse events since the last visit and during this visit
- Collect vital signs (pulse, blood pressure, temperature and respiration rate) pre-treatment
- Conduct pretreatment measurements in both eyes by UHR-OCT and Keratograph 5M (at approximately the same time as conducted at Visit 1) immediately prior the administration of study medication. UHR-OCT will be conducted first, immediately followed by Keratograph 5M.
- Subjects will be assigned a treatment number at this visit.
- Administer one drop of assigned study medication in each eye immediately after the pretreatment assessment (the drug administration will be conducted by the PI or clinical site personnel). NOTE: Remove study medication from refrigerator at least 15 minutes prior to administration.
- At approximately 5 minutes after drug administration, administer drop instillation comfort assessment
- Repeat assessments by UHR-OCT and Keratograph 5M post dose at 15 ± 5 minutes, 30 ± 10 minutes, 1 hour ± 20 minutes, 2 hours ± 30 minutes, 4 hours ± 30 minutes, and 6 hours ± 30 minutes.
- Immediately prior to the 2 hour time point for tear volume measurement, a post instillation dry eye symptom assessment will be completed
- After the 6-hour tear volume assessment, conduct a biomicroscopy and external examination
- At the end of the visit, the subject will be instructed to return to the clinic between 7 and 14 days for the second treatment (Visit 3, Second Treatment Visit) with the visit occurring in the AM, at approximately the same time of day as Visit 1 and Visit 2
- The subjects will be instructed to maintain the same medications and study restrictions between visits to continue being eligible to remain in the study. Subjects will be reminded not to use ocular medications or wear contact lenses on the day of Visit 3

6.3 Visit 3: Second Treatment Visit (7-14 days after Visit 2)

- Subjects will be asked to remain on site through this visit and limit use of devices with video display screens.

- Confirm continued eligibility through review of inclusion and exclusion criteria as outlined in [Sections 5.1 and 5.2](#) of the protocol with the exception of the inclusion criteria #5 (UHR-OCT dry eye).
- Review of concomitant medications and medical changes since last visit
- Administer symptom questionnaires (SPEED, OSDI, and SANDE Part 1 and Part 2) before other procedures and before dosing
- Assess adverse events since the last visit and during this visit
- Collect vital signs pre-treatment (pulse, blood pressure, temperature and respiration rate)
- Conduct pretreatment measurements in both eyes by UHR-OCT and Keratograph 5M in the AM (at approximately the same time as conducted at Visit 1) immediately prior the administration of study medication. NOTE: throughout the study, UHR-OCT will be conducted first, immediately followed by Keratograph 5M.
- Administer one drop of assigned study medication in each eye immediately after the pretreatment assessment (the drug administration will be conducted by the PI or clinical site personnel). NOTE: Remove study medication from refrigerator at least 15 minutes prior to administration.
- At approximately 5 minutes after drug administration, administer drop instillation comfort assessment
- Repeat assessments by UHR-OCT and Keratograph 5M post dose at 15 ± 5 minutes, 30 ± 10 minutes, 1 hour ± 20 minutes, 2 hours ± 30 minutes, 4 hours ± 30 minutes, and 6 hours ± 30 minutes.
- Immediately prior to the 2 hour time point for tear volume measurement, a post instillation dry eye symptoms assessment will be completed
- After the 6-hour tear volume assessment, conduct a biomicroscopy and external eye examination
- At this point, the subject will be discharged from the study.
- Subjects may resume previously used ocular medications when discharged from the study.

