2.2.2 Absorption, Distribution, Metabolism, and Excretion

The absorption, distribution, metabolism, and excretion profile of P-321 was characterized in *in vitro* and *in vivo* studies. P-321 was not metabolized in plasma from different species (rat, rabbit, dog and human) or by incubation with rat and dog hepatocytes.

Oral administration of P-321 to rats did not produce measurable plasma drug concentrations, suggesting that P-321 is not orally available.

The PK and systemic clearance of P-321 was characterized in rats following intravenous (IV) administration. P-321 displayed biphasic elimination from plasma with a long terminal half-life and a high volume of distribution. The PK of P-321 in plasma showed no difference among sex, and no accumulation was observed after multiple days of IV administration.

The renal elimination of P-321 and its potential for inhibition of ENaC in the kidney was studied in rats treated with P-321 by topical ocular administration or by IV infusion. The amount of P-321 recovered in urine over 24 hours following IV and ocular administration accounted for only a small fraction of the total dose administered corresponding to 0.57-1.3% and 0.19%, respectively. Ocular administration of P-321 Ophthalmic Solution in dogs given four times per day over multiple days also indicated that very low amounts of P-321 were excreted in the urine and these concentrations of drug were not associated with changes in urine electrolyte excretion, the most sensitive measurement of the effect of ENaC blockers in the kidney.

The ocular distribution and PK following topical ocular administration of P-321 was assessed in Dutch Belted rabbits following a single dose of 0.1% P-321 Ophthalmic Solution or during QID administration for 14 days. The ocular distribution of P-321 was limited only to the external surface of the eye. P-321 had a long terminal half-life in tears of approximately 24 hours. Sustained drug levels were also observed in the palpebral and bulbar conjunctiva and eyelids for up to 48 hours following a single administration. After multiple days of QID dosing, P-321

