8.1.4 Analysis of Safety

All safety data collected on or after the date that study medication was first dispensed up through the date of the final post dose assessment will be summarized.

The objective of the statistical analysis of the safety parameters is to investigate the data for any effects of study medication on clinical tolerability. All such parameters will be summarized by treatment group and time point as indicated below. Because this study, is a cross over design and, at the cross over treatment, the subjects may no longer be treatment naive, analysis will check for sequence/period effects. If sequence/period effects are detected, the analysis of safety will use just the first period results. Provided that no sequence/period effects are seen, analysis will use the most-recent treatment received as the treatment group.

In the absence of any predefined hypotheses, the general strategy of the safety analysis will be to examine the data summaries for any trends amongst the treatment groups. No formal hypothesis testing will be carried out.

The incidence of AEs will be tabulated by treatment group overall, by treatment sequence, by severity, and relationship to study medication.

Change from baseline values (or shifts from baseline, if more appropriate) will be presented for other safety measures for the visits at which they are assessed.

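### Adverse events are sought for 7-14 days after the first dose but about 6-7 hours after the second, so the Section 8.1.4 period check can be triggered by window length alone and discard all second-period safety data

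*Combined protocol and SAP*

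**What the plan says.** **Collection.** Section 6.3 and the Appendix I schedule place Visit 3 at 7 to 14 days after Visit 2. The AE instruction at Visit 3 is "Assess adverse events since the last visit and during this visit", so the first treatment's window covers the rest of Visit 2 and the whole wash-out. After the Visit 3 dose, tear measurements end with "2 hours ± 30 minutes, 4 hours ± 30 minutes, and 6 hours ± 30 minutes". Biomicroscopy follows, and then "At this point, the subject will be discharged from the study". Section 4.3 puts the treatment visits at about 7 hours. Appendix I has no later contact for completers, and the Early Termination Visit in Section 6.4 is only for withdrawn subjects. Section 10.2 follows non-serious AEs that are unresolved at the last visit but does not ask about new ones.

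**Analysis.** Section 8.1.4 covers safety data "up through the date of the final post dose assessment will be summarized". It looks for sequence or period effects and, if any are detected, uses the first period only. Otherwise, "analysis will use the most-recent treatment received as the treatment group". AE incidence is tabulated by treatment, sequence, severity and relationship. The section gives no criterion for detecting a period effect, says that safety will not be formally tested, and sets no common post-dose window and no adjustment for observation time.

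**Persistence.** Section 2.2.2 reports that in rabbits "P-321 had a long terminal half-life in tears of approximately 24 hours", with drug in the conjunctiva and eyelids for up to 48 hours after one dose.

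**The concern.** Incidence is compared between periods whose observation times differ by more than an order of magnitude. If unrelated illness arises at a steady rate, almost all of it will be recorded after the first dose, whichever treatment that was. The rule in Section 8.1.4 can read this as a period effect and respond by dropping the second period. The crossover then becomes a between-subject safety comparison with half the exposures, for a reason unrelated to the drug.

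If no effect is declared, the treatment tables mix long and short windows without saying so. A reader could also take a low AE count after second-period P-321 as evidence about late tolerability, when late events were not sought.

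**Working it through.** **1. The plan's own figure.** Section 4.3 gives a maximum duration of 23 days. The maximum screening interval is 9 days and the maximum wash-out is 14 days: 9 + 14 = 23. The figure leaves 0 days after Visit 3, which agrees with same-day discharge.

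**2. Windows.**
- After the first dose: 7 × 24 = 168 h to 14 × 24 = 336 h.
- After the second dose: about 6 h to the last assessment, with 7 h as an upper figure from the stated visit length.
- Ratio: 168/7 = 24 to 336/6 = 56.
- Second period's share of post-dose time, at 6 h: 6/(168 + 6) = 3.4% to 6/(336 + 6) = 1.8%.

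**3. Period difference with no drug effect.** The documents give no AE rate. Assume one unrelated AE per 60 person-days, with a range of one per 30 to one per 120, and 24 subjects.
- After the first dose: 24 × 7/60 = 2.8 to 24 × 14/60 = 5.6 expected events. Over the full range: 24 × 7/120 = 1.4 to 24 × 14/30 = 11.2.
- After the second dose, at 6 h: 24 × (6/24)/60 = 0.1. Over the full range: 0.05 to 0.2.

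A table showing several events in period 1 and none in period 2 is therefore the expected result when nothing is wrong.

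**4. What the fallback removes.** With 24 subjects and 1:1 sequences, 12 of the 24 P-321 exposures and 12 of the 24 placebo exposures fall at Visit 3. Keeping the first period leaves about 12 against 12, between subjects.

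**5. Treatment comparison at the review of about 8 subjects.**
- Split 4:4, 7-day wash-out: each treatment has 4 × 168 + 4 × 6 = 696 h. The ratio is 1.
- Split 5:3, 7-day wash-out: 5 × 168 + 3 × 6 = 858 h against 3 × 168 + 5 × 6 = 534 h. The ratio is 1.61.
- Split 5:3, 14-day wash-out: 5 × 336 + 3 × 6 = 1,698 h against 3 × 336 + 5 × 6 = 1,038 h. The ratio is 1.64.
- Expected excess at one per 60 person-days: (858 - 534)/24/60 = 0.23 events, and (1,698 - 1,038)/24/60 = 0.46 events.
- Over the assumed range of rates: 0.11 events (7 days, one per 120) to 0.92 events (14 days, one per 30).

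**6. Late events on P-321.** Only the 12 first-period exposures are asked about events after the visit day. If none is seen, the one-sided 95% upper bound on late risk is 1 - 0.05^(1/12) = 22%. With 24 followed exposures it would be 1 - 0.05^(1/24) = 12%.

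**The case against.** **The fallback restores equal windows.** In the first period P-321 and placebo are both followed for 7-14 days, so if the distortion shows, the existing rule removes it from the treatment comparison. This stands, and that comparison should be kept. But the rule has no detection criterion, and it buys equal windows by discarding the second period, whose visit-day data are comparable between periods.

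**A reader might infer that the P-321 versus placebo comparison is biased.** The documents do not support that in general. Allocation to sequence is 1:1 (Sections 4.1 and 7.1), so the short window falls equally on both treatments in expectation. Distortion needs unbalanced sequences. The documents state no block structure, so the likelihood of imbalance cannot be given, and step 5 shows that its effect is small.

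**A reader might infer that half the P-321 exposures are essentially unfollowed.** That goes too far. Comfort at 5 minutes, symptoms before the 2-hour measurement and biomicroscopy after 6 hours are collected equally in both periods. Unresolved AEs and serious AEs are followed further, and Section 13.2 gives subjects a 24-hour telephone number. What is missing is scheduled enquiry about new late events.

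**A reader might infer from the 24-hour half-life that most of the drug is still in the tears at discharge.** It is a terminal half-life in rabbits, and it says nothing about how much of the drop is lost earlier. Only the persistence of some drug is supported.

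**The decision weight is limited.** The safety analysis is descriptive, and events are classified and tabulated by relationship. The Data Review Group sees AEs, but its written safety conditions in Section 6.5 and Appendix XIV concern serious events and do not compare counts. This stands and keeps the point modest.

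**Conclusion.** The point holds as a cheap improvement to the safety analysis. The unequal windows follow directly from the visit schedule. The main defect is in the rule: Section 8.1.4 tests for a period effect using data in which window length alone can produce one, and then gives up half the exposures if it appears. Secondary effects are treatment tables that mix unequal windows, and no active search for late events after the second dose although the rabbit data show some drug persisting to 48 hours.

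The expected counts rest on the assumed background rate and its constancy over time. The 12-of-24 figure rests on exactly 24 completers with balanced sequences. The window ratio rests only on the visit schedule. None of this shows that the pooled treatment comparison is biased in expectation or that the dose decision would change.

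**What to change.** In Section 8.1.4, define one common window: onset from dosing to the end of the 6-hour assessments of that visit. Use it for the sequence/period check and for the two-period AE comparison, including the table given to the Data Review Group.

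Alongside it:
- keep the full-window AE tables;
- show the first-period P-321 versus placebo comparison over 7-14 days, where the windows are equal;
- list wash-out events by days since dose;
- state in the report that treatments given second had about 6-7 hours of AE collection, so late events after them were not sought.

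Section 10.2 already puts date and time of onset on the CRF, so no new data are needed. The cost is one window definition and one or two extra tables or listings. The downside is that the two-period comparison covers a short window. It recovers no late event after Visit 3, which no analysis of the data as collected could do.
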